5.5 Study Stopping Criteria

If any of the following occur, administration of HS-130/HS-110 will be temporarily or permanently stopped, pending a review by the Safety Review Committee. During that time, no drug can be administered to any patient, until a decision is made.

- Any Death (other than progressive disease) that is at least possibly related to the study agent(s)
- Occurrence of two or more grade 4 events that are at least possibly related to the study agent(s)

Conditions that may warrant trial termination are listed in Section 4.5.

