The first cohort will employ an accelerated design to evaluate the first 4 dose levels in single patients. There will be a staggered enrollment with a minimum 1-week delay between each patient in cohort 1. If any drug-related \geq Grade 2 (other than Grade 2 injection site reaction with pain) event occurs during the first cycle of treatment, the study will revert to 3+3 design starting at that dose level.

Subsequent cohorts in the dose escalation phase will enroll patients following the standard 3+3 design. Three patients will be enrolled in each subsequent dose cohort and enrolled with a (minimum) 1-week staggered delay (i.e. Patient 2 to be dosed \geq 1-week after Patient 1 received the first dose, and Patient 3 to be dosed \geq 1-week after Patient 2 received the first dose).

In the 3-patient cohorts (i.e. 3 patients treated at the same dose), if 1 out of 3 patients experience a DLT during the first two treatment cycles, the dose cohort will be expanded up to 6 patients. If \geq 2 out of 6 patients experience DLTs, the MTD has been exceeded, and dose escalation will cease. Up to 3 additional patients will be enrolled at the next lowest dose if only 3 patients were treated at that dose level, to confirm safety of that dose. If a DLT is observed already with the first patient in Cohort 1, the Safety Review

Committee (Section 8.1.2.8.1) may suggest and approve a dose de-escalation cohort with at least 50 % reduction of HS-110 and HS-130 (dose level -1).

Once all patients in a cohort have completed the first two cycles of dosing and received at least 2 doses of HS-130/HS-110, the safety and tolerability of the combination treatment administered will be reviewed by the safety review committee (SRC). If 0 out of 3 patients or 1 out of 6 patients experience a DLT, then the SRC may recommend enrollment at the next higher dose level.

Any patient who does not receive two doses of the study treatment during the DLT window of observation (first 2 cycles/4 weeks), for reasons other than study drug-related toxicity and did not experience a DLT will not be taken into account in the assessment of the overall DLT rate for the particular dose level cohort and will be replaced.

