- i: Approximately 23 mL blood per draw Day 1 (pre-dose) and Day 8 for C1 and C2, and at 30-day safety follow-up visit for immune response labs (See Section 8.6).
- j: Cytokines and chemokines sample collection on Day 1 for C1 and C2 at time-points: Before HS130/HS110 treatment, and 2 hr ± 10 minutes after treatment. For C3 and beyond only if the patient is symptomatic i.e. flu-like symptoms, fever, or allergic reactions. (Approximately 3 mL blood per draw).
- k: Pre-treatment biopsy (archival tissue may be submitted if collected less than 6-months prior to C1D1 and the local pathologist confirms that an adequate amount of tissue/tumor cells exist to allow completion of all testing as outlined in the Specimen Collection Manual) and on-treatment biopsy collected within 5-14 days after patient completes 2nd dose of HS-130/HS-110 for genomic and proteomic analysis of exploratory biomarkers (e.g. mIHC). Biopsy should be collected for patients with accessible tumor lesions, incl. metastases (e.g. lymph node metastases) where it is considered feasible without a risk of complications for the patient. Coagulation parameters and blood cells should be assessed and reviewed per institutional standard prior to any biopsy.
- l: HS-130 and HS-110 will be administered via intradermal injections/re-injections (up to 10 total) on Day 1 of each cycle, depending on the assigned dose level. (See section 6.1 Drug preparation and administration)
- m: All assessments should be performed at 30 days ± 3 days after the last treatment, during the 30-day safety follow-up visit.
- n: If a patient stops treatment for any other reason than progressive disease, radiological assessments will continue every 12 weeks starting from the date of patient's last dose until disease progression or initiation of new anti-cancer treatment.
- o: Survival status and subsequent anti-cancer therapy information will be collected approximately every 12 weeks in a clinic visit, or by telephone from the time of disease progression or initiation of new anti-cancer treatment until death.
- p: Each cycle is 14 days.

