9.3 Safety

Safety will be assessed by means of physical examination, weight, vital signs, performance status, laboratory evaluations (hematology, biochemistry, cytokines and chemokines), electrocardiogram (ECG), and recording of concurrent illness/therapy and treatment-emergent adverse events. CTCAE version 5 will be used to grade all toxicities. Patients will also be monitored for any clinical symptoms associated with elevated cytokines levels. All related adverse events will be monitored until resolution. Patients will be monitored for safety and concomitant medications throughout the study.

Safety data will be summarized for the safety evaluable population. These data will include AEs and laboratory parameters. Adverse event terms will be coded using the most current version of Medical Dictionary for Drug Regulatory Activities (MedDRA®).

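### In single-patient levels 1–4 the next level may open after one week, inside the plan's own 14-day reversion window, and a Cycle 2 DLT at levels 2–4 triggers no set escalation step

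*Combined protocol and SAP*

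**What the plan says.** **Spacing.** Table 2 (Section 6.1.1) places levels 1–4 in cohort 1 with a minimum of one patient each. The stated interval is: "There will be a staggered enrollment with a minimum 1-week delay between each patient in cohort 1". The Synopsis says the same.

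**Reversion.** The trigger is a drug-related toxicity of Grade 2 or higher, with painful Grade 2 injection site reactions excepted. If such an "event occurs during the first cycle of treatment, the study will revert to 3+3 design starting at that dose level". Cycles last 14 days. The DLT window is two cycles, or 4 weeks.

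**Timed review.** The SRC review with a stated time comes "Once all patients in a cohort have completed the first two cycles of dosing and received at least 2 doses of HS-130/HS-110". Its escalation condition is 0 of 3 or 1 of 6 patients with a DLT. The Synopsis and Section 8.1.2.8.1 also say that the SRC will evaluate data at each dose level and recommend escalation, reduction, a halt or more patients. They state no follow-up time.

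**DLT rules.** The expansion rule begins: "In the 3-patient cohorts (i.e. 3 patients treated at the same dose), if 1 out of 3 patients experience a DLT". Dose level -1 is an option only if the first patient in cohort 1 has a DLT. Section 6.1.2 requires immediate notification of a suspected DLT and leaves an ad hoc SRC meeting to the Sponsor. Section 6.2 delays dosing for DLT-equivalent toxicity. Section 5.5 suspends treatment after a possibly related death or two or more possibly related Grade 4 events; in that period "no drug can be administered to any patient, until a decision is made".

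**Safety sampling.** Table 3 and Section 7.3 schedule hematology and chemistry at Cycle 1 Day 1 and next at Cycle 2 Day 1 (±2 days). Table 3 footnote j adds "Cytokines and chemokines sample collection on Day 1 for C1 and C2 at time-points" before and 2 hours after dosing, and Section 9.3 counts these among the safety laboratory evaluations. Day 8 (±2 days) is a clinical visit with immune-response blood only.

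**The concern.** With one patient per level, each step rests on what has been seen in the patient below. The plan chose a 14-day period in which a Grade 2 event ends single-patient escalation, yet its spacing rule lets the next level be dosed halfway through that period. An event in the second week would still force reversion at the lower level, but the higher level could already have been given.

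The second gap concerns the second dose. A Cycle 1 Grade 2 event forces 3+3, while a Grade 3 or single Grade 4 DLT after the second dose at levels 2–4 forces no set step. The plan gives reasons to expect later effects: Section 2.5 says the immune response needs time to develop, and Section 2.3.1 reports increased boost responses in mice. HS-130 is first-in-human, and Section 2.3.2 says no formal GLP toxicology has been done. Clinical experience with HS-110 does not cover secreted OX40L-Ig.

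**Working it through.** **Inputs.** Minimum stagger 7 days, trigger window 14 days, DLT window 28 days, dosing every 14 days (Section 6.1.1); first post-dose hematology and chemistry 14 ± 2 days after the first dose (Table 3); doses from Table 2.

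**The plan's own figures.** Minimum sample size: 4 × 1 + 3 × 3 = 13, as stated. DLT window: 2 × 14 = 28 days, as stated.

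**Floor calendar.** The first dose at level k falls on Day 1 + 7(k − 1): Days 1, 8, 15 and 22. At each step the patient one level below has 7 of 14 trigger days, 7 of 28 DLT days, 1 of 2 doses and no scheduled post-dose hematology or chemistry. That sample falls 12 to 16 days after dosing, so it is still 5 to 9 days away. The Day 8 visit can fall up to 2 days after the next level is dosed.

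**Higher-level doses inside an open DLT window, at the floor**

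| Window | Days | Higher-level doses | Total | At a higher OX40L-Ig dose |
|---|---|---|---|---|
| Level 1 | 1–28 | L2 Days 8, 22; L3 Day 15; L4 Day 22 | 4 doses, 3 patients | 4 doses, 3 patients |
| Level 2 | 8–35 | L3 Days 15, 29; L4 Day 22 | 3 doses, 2 patients | 1 dose, 1 patient |
| Level 3 | 15–42 | L4 Days 22, 36 | 2 doses, 1 patient | 2 doses, 1 patient |

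The last column uses the HS-130 doses of 150, 300, 300 and 600 ng/24-hr at levels 1–4. Steps 1 to 2 and 3 to 4 raise OX40L-Ig. Step 2 to 3 raises only HS-110, from 150 to 300 ng/24-hr.

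**With a 14-day wait.** First doses fall on Days 1, 15, 29 and 43. Windows 1–28, 15–42 and 29–56 each contain one higher-level dose in one patient (Days 15, 29 and 43). Higher-level doses inside an open trigger window fall from 1 to 0 at each step.

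**Days since the second dose when level 4 opens**

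| Patient | Floor (Day 22) | 14-day wait (Day 43) |
|---|---|---|
| Level 1 | 22 − 15 = 7 | 43 − 15 = 28 |
| Level 2 | 22 − 22 = 0 | 43 − 29 = 14 |
| Level 3 | second dose due Day 29 | 43 − 43 = 0 |

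So the wait protects the trigger window. It does not by itself give follow-up after the second dose in the patient one level below.

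**Rules tested against one Grade 3 or Grade 4 DLT in Cycle 2 at levels 2–4**

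- Reversion: Cycle 1 only, so not met.
- 1 of 3 and 2 of 6: three-patient cohorts only, so not met.
- Dose level -1: first patient only, so not met.
- Section 5.5: needs a related death or at least two related Grade 4 events, so not met.
- Timed review: its 0 of 3 or 1 of 6 condition has no counterpart for one patient.

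**Mouse reference.** Section 2.3.2 gives a NOAEL for mHS-130 of 387.2 ng/24-hr per animal. The start is 387.2 / 150 = 2.6-fold below it, which agrees with Section 2.5. Levels 2 and 3 (300 ng) are also below it. Level 4 is above it: 600 / 387.2 = 1.5. These are absolute doses with no body-size adjustment.

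**The case against.** The strongest reply is that the SRC already controls each step. It will evaluate every dose level and may hold, lower or add patients, and one week is a minimum stagger, not an instruction to escalate. That stands, and it makes the calendar above a floor that needs SRC agreement and enrollment exactly every 7 days. It does not supply a minimum follow-up or a criterion for one patient.

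A second reply reads "Once all patients in a cohort have completed the first two cycles of dosing and received at least 2 doses of HS-130/HS-110" level by level, which would impose about 28 days per step. Table 2 groups levels 1–4 as one cohort, and the 1-week stagger would then do nothing in that phase.

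The risk offsets are also real: a MABEL-based start with a stated safety factor above 100-fold, over 100 patients treated with HS-110, and 4.7 million cells at level 4 against 10 million HS-110 cells weekly in the earlier study. Three levels lie below the absolute mHS-130 NOAEL, although the figure for human HS-130 cells in mice is lower, at 219.5 ng/24-hr.

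A reader might infer more than the documents support:

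- *All three steps are equally exposed to the new component.* They are not; step 2 to 3 leaves HS-130 unchanged.
- *No safety laboratory data exist before the next step.* The 2-hour cytokine sample does; what is missing is hematology and chemistry.
- *A Cycle 2 DLT goes unanswered.* Notification and a Sponsor decision on an SRC meeting are mandatory, dosing is to be delayed in that patient, and adding patients is a named SRC option.
- *A level 4 DLT could pass unreviewed to level 5.* The two-cycle SRC review of cohort 1 comes first.

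**Conclusion.** The concern holds in this form. The stated minimum spacing is shorter than the plan's own trigger window, and a Cycle 2 DLT in a single patient at levels 2–4 has no set escalation or expansion consequence. The second gap matters most at levels 2 and 3, because level 4 meets the timed review before level 5, even though that review has no rule for one patient.

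The exposure is limited to three steps, two of which raise OX40L-Ig. The dose counts assume the 7-day minimum at every step, no SRC hold, visits on nominal days, and Table 2's meaning of cohort. They show what the wording allows; nothing in the documents supports reading them as an expected course. The point should be fixed because the remedy is a clear rule at modest cost in time.

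**What to change.** Amend Section 6.1.1 and the Synopsis:

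1. Do not dose the next single-patient level until the previous patient has completed Cycle 1 (at least 14 days, with the Cycle 2 Day 1 pre-dose hematology and chemistry read) and the SRC has reviewed that level.
2. Any DLT in Cycle 1 or Cycle 2 at a single-patient level reverts the study to 3+3 at that level, and pauses new and repeat dosing at higher levels pending SRC review.

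Keep the dose level -1 option and Section 5.5 as they are. Part 1 closes the trigger window before each step; part 2 covers events after the second dose. With both, at most one patient is exposed at a higher level when a Cycle 2 DLT occurs. That patient has had one dose on the nominal schedule and up to two with the −2-day visit window: level 2 starts on Day 15, its second dose may fall on Day 27, and level 1's window runs to Day 28.

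**Time.** Level 4 opens at least 43 − 22 = 21 days later. With each Cycle 2 Day 1 at +2 days the starts are Days 1, 17, 33 and 49, so the delay is 49 − 22 = 27 days. Lab and SRC turnaround, which the plan does not state, come on top. A full 28-day wait would cost 85 − 22 = 63 days.

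**Patients.** None extra unless the extended trigger fires. With one DLT, no further expansion, dose level -1 unused, patients already dosed counted at their level, and escalation to level 7, the totals against 13 are:

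- level 4: 3 + 6 + 9 = 18
- level 3: 2 + 6 + 3 + 9 = 20
- level 2: 1 + 6 + 3 + 3 + 9 = 22
- level 1: 6 + 3 + 3 + 3 + 9 = 24

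These lie within 13–30, but further expansion could exceed 30. With six patients at every 3+3 level, reverting at level 4 gives 3 + 4 × 6 = 27, and reverting at level 3 gives 2 + 5 × 6 = 32.

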2.4 Previous Clinical Studies

There are no previous clinical studies with HS-130.

HS-110 has been studied in humans and to date, over 100 patients with non-small cell lung cancer have been treated with HS-110 with over 1000 doses of HS-110 administered intradermally (IND No. 14814). The standard dose of HS-110 in the phase 1/2 study NCT02439450 is 1×10^7 viable cells/0.5 mL, administered as 5 (0.1 mL) intradermal injections weekly for 18 weeks (Arm 5), or weekly for 13 weeks followed by every 3 weeks boost dosing until progressive disease (Arm 6).

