6.0 TREATMENT OF SUBJECTS

6.1 Drug Preparation and Administration

Both HS-130 and HS-110 drug products will be administered via intradermal injections/re-injections based on the dose levels as defined in the dose escalation scheme (Section 6.1.1) on Day 1 of each cycle.

If any serious adverse reaction occurs these may be treated per institutional practice, as noted in Section 6.4 Concomitant Medication.

The HS-130 final drug product is packaged in single-dose vials as fully-diluted frozen liquid filled under aseptic conditions in 1.2 mL cryovials, containing 0.6 mL suspension of 2×10^7 cells/mL (targeted) in a cryopreservative buffer, with a final formulation of 0.567% sodium chloride, 0.5% human serum albumin (HSA), 0.007% sodium bicarbonate, 6% pentastarch, and 5% dimethyl sulfoxide (DMSO).

HS-110 (viagenpumatulcel-L) is packaged in single-dose vials as fully-diluted frozen liquid filled under aseptic conditions in 1.2 mL cryovials, containing 0.6 mL suspension of 2×10^7 cell/mL (targeted) in a cryopreservative buffer, with a final formulation of 0.567% sodium chloride, 0.5% HSA, 0.007% sodium bicarbonate, 6% pentastarch, and 5% DMSO.

Each patient will be administered up to a total of 10 spatially divided intradermal injections/re-injections of ≤ 0.14 mL per injection, depending on the required HS-130 and HS-110 dose levels. HS-130 will be injected first, and a period of no less than 2 minutes, but no more than 5 minutes, should elapse before administering HS-110. HS-110 must be injected into the same exact location as the HS-130 injections (re-injected sites). There are some dose levels (3, 5, 6, and 7) where the number of HS-110 injections will exceed the number of HS-130 injections. In these cases, after all HS-130 sites have been re-injected, the HS-110 may be administered in a new spatially divided injection site.

At each cycle, the injection region will alternate between the left shoulder and right shoulder. The HS-130 and HS-110 injections will all be administered into the designated injection region for that cycle (left shoulder or right shoulder) to increase volume distribution and enhance antigen presentation to lymph node regions.

Table 1: HS-130/HS-110 Dose Administration Guidelines

Dose Level	Study Drug	Total mL	Volume (mL) per Injection							
			Injection #1	Injection #2	Injection #3	Injection #4	Injection #5	Injection #6	Injection #7	
-1	HS-130	0.02	0.02							
	HS-110	0.06	0.06							
1	HS-130	0.04	0.04							

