	HS-110	0.10	0.10							
2	HS-130	0.10	0.10							
	HS-110	0.10	0.10							
3	HS-130	0.10	0.10							
	HS-110	0.22	0.12	0.10						
4	HS-130	0.18	0.10	0.08						
	HS-110	0.22	0.12	0.10						
5	HS-130	0.18	0.10	0.08						
	HS-110	0.44	0.12	0.12	0.10	0.10				
6	HS-130	0.36	0.12	0.12	0.12					
	HS-110	0.44	0.12	0.12	0.10	0.10				
7	HS-130	0.36	0.12	0.12	0.12					
	HS-110	0.86	0.14	0.12	0.12	0.12	0.12	0.12	0.12	0.12

Drug products will be supplied to clinical sites via shipments in liquid nitrogen dry-shipper units, which will be validated to maintain cryogenic temperatures for up to 10 days. Upon arrival, the products will be transferred to controlled liquid nitrogen storage at the clinical site in the liquid nitrogen vapor phase until ready for preparation. Study staff must take care to minimize temperature excursions during transfer of the product from shipping containers to controlled liquid nitrogen storage on site.

Drug products will not be retrieved from cryogenic storage until the study subject is present and available for dosing. When removing a product carton from storage to retrieve a vial for dosing, any doses remaining in the carton will be returned to cryogenic storage immediately. Study drugs must be administered within 2 hours of retrieval from the dewar (cryogenic storage).

Stability studies for HS-130 are currently ongoing and clinical sites will be notified of storage information and/or shelf life change. The instructions for preparation, administration, stability and storage of HS-110 to be used in combination with HS-130 will reference instructions per the Investigational Product Manual.

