6.1.1 Dose Escalation Scheme

Escalating doses of the viable, replication-incompetent, human whole cell vaccines, HS-130 and HS-110 will be administered to patients via intradermal injections/re-injections (up to 10 total) on Day 1 of a two-

week cycle. The length of each cycle is two weeks, and the DLT window of observation includes the safety data obtained from the first two treatment cycles, Cycle 1 and Cycle 2 (4 weeks).

Seven dose levels will be explored, and patients will receive separate escalating doses of HS-130 and HS-110 in alternating fixed 1:1 or 2:1 ratio based on the amount of secreted OX40L-Ig (HS-130) and gp96-Ig fusion protein (HS-110) per cell of the drug product. The starting dose of HS-130/HS-110 combination is based on the dose-ranging studies conducted in animal models of T cell expansion and tumor challenge, as well as established clinical experience from HS-110.

Table 2: HS-130/HS-110 Dose Levels

Cohort	Dose level	HS-130 dose* (ng/24-hr OX40L-Ig)	HS-110 dose* (ng/24-hr gp96-Ig)	HS-130: HS-110 Ratio	Total number of AD100 cells (Q2W) [#]	Minimum number of patients
1	-1	75 ng/24-hr	75 ng/24-hr	1:1	1.0 million	1
	1	150 ng/24-hr	150 ng/24-hr	1:1	1.9 million	1
	2	300 ng/24-hr	150 ng/24-hr	2:1	2.3 million	1
	3	300 ng/24-hr	300 ng/24-hr	1:1	3.8 million	1
	4	600 ng/24-hr	300 ng/24-hr	2:1	4.7 million	1
2	5	600 ng/24-hr	600 ng/24-hr	1:1	7.6 million	3
3	6	1,200 ng/24-hr	600 ng/24-hr	2:1	9.3 million	3
4	7	1,200 ng/24-hr	1,200 ng/24-hr	1:1	15.1 million	3

*The number of cells administered to achieve the HS-130 (ng/24-hr of OX40L-Ig protein) and HS-110 (ng/24-hr of gp96-Ig protein) dose will be determined based on the specifications for that batch of the drug product. For HS-130: Lot HBI-HS-130-FP-001 = 241 fg/cell/24-hr and HS-110: Lot 0000748931 = 104 fg/cell/24-hr. The productivity per cell will be determined using the same assay format and standards for pre-clinical and clinical derived material.

[#] The suggested total number of allogeneic tumor cells (AD100) administered every second week at the highest dose level is similar to or less than the weekly dose of 10 million HS-110 cells that has been established safe and immunologically effective in the HS-110 study (NCT02439450, IND No. 14814).

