8.1.2.8 Safety Data Review

8.1.2.8.1 Safety Review Committee

A Safety Review Committee (SRC) comprises of 3 members – one Investigator, a representative from Heat Biologics and the Medical Monitor will evaluate the data obtained at each dose level including a review of all adverse events (serious and non-serious adverse events) as they are reported by the study site. The SRC will recommend whether the dose should be escalated as per protocol, revised to a lower level or

intermediate level, halted altogether or more patients are required at the same dose level to evaluate safety. If a DLT is observed already with the first patient treated in Cohort 1, the SRC may suggest and approve dose de-escalation with at least 50% reduction of HS-130 and HS-110 (dose level -1), depending on the nature of the reaction.

Ad-hoc SRC meetings may be called for by both the SRC and Sponsor any time during the study if DLTs are observed and/or new safety data warrants immediate action to the conduct of the trial (including events defined by the Study Stopping Criteria in Section 5.5).

The conclusion of the SRC meeting will be documented in meeting minutes. The outcome of the SRC meeting will be communicated to all Investigators.

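### Dose level -1 must cut both products by at least 50%, but the Table 1 volumes cut HS-110 by only 40%

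*Combined protocol and SAP*

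**What the plan says.** Section 6.1.1 (Dose Escalation Scheme) provides a fallback below the starting dose. After a DLT in the first Cohort 1 patient, the SRC "may suggest and approve a dose de-escalation cohort with at least 50 % reduction of HS-110 and HS-130 (dose level -1". Section 8.1.2.8.1 (Safety Review Committee) gives the same minimum: "dose de-escalation with at least 50% reduction of HS-130 and HS-110 (dose level -1". Both sections name both products.

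Table 2 in Section 6.1.1 sets level 1 at 150 ng/24-hr of each product and level -1 at 75 ng/24-hr of each, with a 1:1 ratio at both levels.

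Table 1 in Section 6.1 (Drug Preparation and Administration) gives the volumes to inject. For HS-110 the level -1 row reads "HS-110 0.06 0.06" and the level 1 row reads "HS-110 0.10 0.10" (total mL, then mL in the first injection). For HS-130 the level 1 row reads "HS-130 0.04 0.04", and the level -1 total is 0.02 mL. Section 6.1 describes HS-110 as a fully diluted suspension at one targeted concentration, and it is the same for every dose level.

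**The concern.** The reduction rule and Table 2 describe a halving of both products. Table 1 halves only HS-130. A site that follows Table 1 would miss the minimum in Section 6.1.1, and a site that follows Section 6.1.1 would have to depart from Table 1.

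Level -1 is the safety fallback of a first-in-human combination, reached after toxicity at the lowest planned dose. The SRC could approve it believing that both products are at least halved while the site draws up 60% of the previous HS-110 volume. The SRC decision after a first-patient DLT is not the only route to these volumes. Section 6.3 allows a one-level reduction for toxicity along the escalation scheme, which would take a level 1 patient to level -1.

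**Working it through.** **Inputs.** Table 1 totals: HS-130 0.04 mL (level 1) and 0.02 mL (level -1); HS-110 0.10 mL and 0.06 mL. Table 2 doses: 150 and 75 ng/24-hr for each product. Required cut: at least 50% for each (Sections 6.1.1 and 8.1.2.8.1).

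**Step 1: the plan's own figure.** Cut = 1 - (level -1)/(level 1). For the Table 2 doses this is 1 - 75/150 = 50% for both products, so the nominal doses meet the rule.

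**Step 2: the volumes.**
- HS-130: 1 - 0.02/0.04 = 50%.
- HS-110: 1 - 0.06/0.10 = 40%.

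Dose is volume times strength. Within one lot the strength is the same in both rows and cancels, so 40% is the delivered cut whatever the concentration or potency.

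**Step 3: a second check that needs no strength.** Both levels are labelled 1:1, so the ratio of HS-110 to HS-130 volume should be equal. It is 0.10/0.04 = 2.5 at level 1 and 0.06/0.02 = 3.0 at level -1.

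**Step 4: probable cause (inference).** Every Table 1 volume is a multiple of 0.02 mL, although the protocol states no rounding rule. If each HS-110 total was rounded to the nearest 0.02 mL, the strength must lie between dose/(volume + 0.01) and dose/(volume - 0.01) in every row. The tightest bounds are:
- lower, from level 7: 1200/0.87 = 1,379 ng/mL;
- upper, from levels 5 and 6: 600/0.43 = 1,395 ng/mL.

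At 1,379-1,395 ng/mL:
- 75 ng needs 0.0538-0.0544 mL, which rounds up to 0.06;
- 150 ng needs 0.1075-0.1088 mL, which rounds down to 0.10.

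The two roundings go in opposite directions and turn a nominal 50% cut into 40%.

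**Step 5: size in ng, at the inferred strength.** 0.06 mL delivers 82.8-83.7 ng, which is 10-12% above 75 ng. Against the nominal 150 ng the cut is 1 - 83.7/150 = 44.2% to 1 - 82.8/150 = 44.8%, still short of 50%.

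**Step 6: can finer rounding explain it?** Suppose the printed volumes stand for values within 0.005 mL either side. The cut then lies between 1 - 0.065/0.095 = 32% and 1 - 0.055/0.105 = 48%. It never reaches 50%.

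**Step 7: excess volume.** Half of 0.10 mL is 0.05 mL, so the excess is 0.01 mL. That is 0.2 million cells at the targeted 2×10^7 cells/mL. At the inferred strength and 104 ng per 10^6 cells it is about 13.8/104 = 0.13 million.

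**The case against.** The best defence is that the protocol defines dose in ng/24-hr, and on that scale Table 2 halves both products exactly. Table 1 is headed as guidelines, cell numbers are to be set from batch specifications, and HS-110 preparation refers to an Investigational Product Manual that is not among the documents. On this reading the rule is met and a volume guide is coarsely rounded. It is true that the nominal doses comply and that the fault lies only in the volumes. But patients receive the volume, Table 1 is the only volume instruction in the protocol, and a batch adjustment within one lot scales both rows equally and leaves 40%. An unseen manual cannot be assumed to override the printed figures.

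A second argument is that the SRC only may open level -1 and may also choose another lower or intermediate level. That discretion covers whether level -1 is used. Once it is used, the 50% minimum applies.

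Three further points stand as qualifications. Part of the gap arises at level 1, where 0.10 mL delivers about 138-140 ng at the inferred strength, 7-8% below nominal. The inferred strength is about one third below the targeted concentration times the lot productivity (20 million cells/mL × 104 ng per million = 2,080 ng/mL), so the ng figures are illustrative. The range in Step 6 describes what the printed figures could stand for, not what staff would draw up.

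**Conclusion.** The concern holds. Table 1 cuts HS-110 by 40% where Sections 6.1.1 and 8.1.2.8.1 require at least 50%; HS-130 is cut by exactly 50%. The 40% rests only on the printed volumes and on the same HS-110 lot being used at both levels. The rounding explanation and every ng figure for a volume rest on the inferred 1,379-1,395 ng/mL.

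The practical weight is modest. The excess is 0.01 mL, in a level that may never open. HS-130, the only product not previously given to humans, is halved. For HS-110, Section 2.4 gives the standard dose as 1×10^7 "viable cells/0.5 mL, administered as 5 (0.1 mL) intradermal injections weekly for 18 weeks (Arm 5", so 0.06 mL is 0.06/0.5 = 12% of an established dose. No endpoint or MTD rule is affected. It should still be corrected, because a dosing figure contradicts a stated safety rule.

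**What to change.** In Table 1, change the level -1 HS-110 volume from 0.06 mL to 0.05 mL or less, and leave the 50% rule as it is.

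- **0.05 mL (preferred).** Cut = 1 - 0.05/0.10 = 50%, and the volume ratio returns to 0.05/0.02 = 2.5, as at level 1. At the inferred strength it delivers 69.0-69.8 ng, 7-8% below 75 ng and closer than the present 10-12% above. The sponsor should confirm that this volume can be drawn up reliably, since it leaves the 0.02 mL steps.
- **0.04 mL (if 0.02 mL steps must be kept).** Cut = 1 - 0.04/0.10 = 60%. Table 1 already uses this volume for HS-130. It delivers about 55-56 ng, roughly 26% below 75 ng, so it meets the rule but agrees less well with Table 2.

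Raising level 1 to 0.12 mL would also restore 50% (1 - 0.06/0.12), but it increases the starting dose and forces the same change at level 2, which shares the 150 ng HS-110 dose and the 0.10 mL volume.

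A Table 1 footnote giving the delivered dose at each level after rounding would be a useful addition. The cost is one table cell and the matching pharmacy instruction, with no added patients, visits or procedures.
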